7.2.3 Pharmacokinetics and immunogenicity assessments

Serial blood samples will be collected at specified time points as outlined in in [Table 7-8](#), [Table 7-9](#), [Table 7-10](#) and [Table 7-11](#) to measure NIR178 and its metabolite, NJI765, PDR001 and anti-drug antibodies (ADAs). Blood samples should be collected from the arm opposite from the study drug infusion, or from another site. Complete instructions for sample processing, handling and shipment will be provided in the [CNIR178X2201 Laboratory Manual].

PK and anti-drug antibody samples will also be collected at the End of Treatment Visit and in the event of a clinically significant AE (such as infusion reaction/anaphylaxis) or if anti-drug antibody is suspected, at which time those samples could be used to measure any relevant biomarkers, to understand the infusion reaction/adverse event better.

The exact date and clock times of study drug administration and blood sample collection will be recorded on the appropriate electronic care report form (eCRF). Any sampling issues should be noted on the eCRF and on appropriate source documentation. If vomiting occurs within 4

[figure not shown]
hours following NIR178 oral administration on dosing days with a pre- and post-dose PK blood collection, the clock time of vomiting should be recorded in the Dose Administration Record (DAR) PK eCRF page. For PDR001, in case the administration is stopped or temporarily paused during infusion, these events should be captured in the appropriate DAR PK eCRF page.

Residual PK and ADA serum or plasma samples used for PK and/or ADA analysis may also be used for exploratory PK and/or PD analyses.

During the COVID-19 pandemic that limits or prevents on-site study visits, or if visits by site staff to a patient's home are not feasible the collection of samples may be modified by Novartis and will be communicated to the Investigator.

Table 7-8 Pharmacokinetic blood collection log for PDR001 and ADA (all study parts and schedules, including Japanese safety run-in and Part 3)

Cycle	Study day	Scheduled time point (Sampling window)	Analytes
1 (Cycle 2 for Japanese safety run-in patients) ^e	1	Pre-dose ^b (0 h)	PDR001 and ADA ^a
1 (Cycle 2 for Japanese safety run-in patients) ^e	1	1 h (± 5 min) post end of C1D1 infusion dose ^c	PDR001
1 (Cycle 2 for Japanese safety run-in patients) ^e	8	168 h (± 8 hr) post dose	PDR001
1 (Cycle 2 for Japanese safety run-in patients) ^e	15	336 h (± 8 hr) post dose	PDR001
1 (Cycle 2 for Japanese safety run-in patients) ^e	22	504 h (± 8 hr) post dose	PDR001
2	1	Pre-dose ^b of cycle 2 (0 h)	PDR001 and ADA ^a
3	1	Pre-dose ^b of cycle 3 (0 hr)	PDR001 and ADA ^a
3	1	1 hr (± 5 min) post end of C3D1 infusion dose ^c	PDR001
3	15	336 hr (± 8 hr) post dose	PDR001
4	1	Pre-dose ^b of cycle 4 (0 h)	PDR001 and ADA ^a
5	1	Pre-dose ^b of cycle 5 (0 h)	PDR001 and ADA ^a
6	1	Pre-dose ^b of cycle 6 (0 h)	PDR001 and ADA ^a
EOT ^d		Anytime	PDR001 and ADA ^a
Unscheduled		Anytime	PDR001 and ADA ^a

Cycle	Study day	Scheduled time point (Sampling window)	Analytes

Blood samples are to be collected from the arm opposite from infusion site, or alternatively, infusion site will need to be flushed with 10 mL of saline.
 
^a Immunogenicity (IG) (Anti-Drug [PDR001] Antibody): blood samples to be collected for anti-drug antibody together with PK samples
 
^b Pre-dose blood samples should be collected prior to start of infusion of any treatment
 
^c PDR001 sampling time is relative to the end of PDR001 infusion
 
^d A PK sample collection will occur at cycle 6 or EOT, whichever occurs first
 
Note: For Japanese safety run-in, PDR001 samples collection will begin from cycle 2 onwards.
 
^e As of protocol amendment 6, patients enrolled in the Japanese safety run-in part will receive NIR178 in combination with PDR001 starting at Cycle 1 and PDR001/ADA PK sample collections will begin at Cycle 1
			

Table 7-9 Pharmacokinetic blood collection log for NIR178: Part 1, Part 2, Part 3 (NIR178 Schedule 1), and Japanese safety run-in

Cycle	Day	Scheduled Time Point (h)	Analyte ^b
1	1	Pre-dose (0 h)	NIR178 and NJI765
1	1	15 min post-dose (\pm 5 min)	NIR178 and NJI765
1	1	30 min post-dose (\pm 5 min)	NIR178 and NJI765
1	1	1 h post-dose (\pm 5 min)	NIR178 and NJI765
1	1	1.5 h post-dose (\pm 5 min)	NIR178 and NJI765
1	1	2 h post dose (\pm 10 min)	NIR178 and NJI765
1	1	3 h post-dose (\pm 10 min)	NIR178 and NJI765
1	1	4 h post-dose (\pm 30 min)	NIR178 and NJI765
1	1	8 h post-dose (\pm 30 min)	NIR178 and NJI765
1	2	Pre-dose (0hr/12 hrs post day 1 evening dose)	NIR178 and NJI765
1	8	Pre-dose (0 h)	NIR178 and NJI765
1	15	Pre-dose (0 h)	NIR178 and NJI765
1	28	Pre-dose (0 h)	NIR178 and NJI765
1	28	15 min post-dose (\pm 5 min)	NIR178 and NJI765
1	28	30 min post-dose (\pm 5 min)	NIR178 and NJI765
1	28	1 h post-dose (\pm 5 min)	NIR178 and NJI765
1	28	1.5 h post-dose (\pm 5 min)	NIR178 and NJI765
1	28	2 h post dose (\pm 10 min)	NIR178 and NJI765
1	28	3 h post-dose (\pm 10 min)	NIR178 and NJI765
1	28	4 h post-dose (\pm 30 min)	NIR178 and NJI765
1	28	8 h post-dose (\pm 30 min)	NIR178 and NJI765
2	1	Pre-dose (0hr/12 hrs post day 28 evening dose)	NIR178 and NJI765
3	1	Pre-dose	NIR178 and NJI765
4	1	Pre-dose	NIR178 and NJI765
5	1	Pre-dose	NIR178 and NJI765
6	1	Pre-dose	NIR178 and NJI765
EOT ^a		Anytime	NIR178 and NJI765
Unscheduled		Anytime	NIR178 and NJI765

^a a PK sample collection will occur at cycle 6 or EOT, whichever occurs first

^b Same blood samples collected to assess PK of NIR178 will be used to measure its metabolite NJI765 as both analytes are assayed simultaneously by the analytical laboratory.

Table 7-10 Pharmacokinetic blood collection log for NIR178 Part 2 (NIR178 Schedule 2)

Cycle	Day	Scheduled Time Point (h)	Analyte ^b
1	1	Pre-dose (0 h)	NIR178 and NJI765
1	1	15 min post-dose (\pm 5 min)	NIR178 and NJI765
1	1	30 min post-dose (\pm 5 min)	NIR178 and NJI765
1	1	1 h post-dose (\pm 5 min)	NIR178 and NJI765
1	1	1.5 h post-dose (\pm 5 min)	NIR178 and NJI765
1	1	2 h post dose (\pm 10 min)	NIR178 and NJI765
1	1	3 h post-dose (\pm 10 min)	NIR178 and NJI765
1	1	4 h post-dose (\pm 30 min)	NIR178 and NJI765
1	1	8 h post-dose (\pm 30 min)	NIR178 and NJI765
1	2	Pre-dose (0hr/ 12 hrs post day 1 evening dose)	NIR178 and NJI765
1	14	Pre-dose (0 h)	NIR178 and NJI765
1	14	15 min post-dose (\pm 5 min)	NIR178 and NJI765
1	14	30 min post-dose (\pm 5 min)	NIR178 and NJI765
1	14	1 h post-dose (\pm 5 min)	NIR178 and NJI765
1	14	1.5 h post-dose (\pm 5 min)	NIR178 and NJI765
1	14	2 h post dose (\pm 10 min)	NIR178 and NJI765
1	14	3 h post-dose (\pm 10 min)	NIR178 and NJI765
1	14	4 h post-dose (\pm 30 min)	NIR178 and NJI765
1	14	8 h post-dose (\pm 30 min)	NIR178 and NJI765
1	15	12 hrs post day 14 evening dose	NIR178 and NJI765
EOT ^a		Anytime	NIR178 and NJI765
Unscheduled		Anytime	NIR178 and NJI765

^a a PK sample collection will occur at cycle 6 or EOT, whichever occurs first

^b Same blood samples collected to assess PK of NIR178 will be used to measure its metabolite NJI765 as both analytes are assayed simultaneously by the analytical laboratory.

Table 7-11 Pharmacokinetic blood collection log for NIR178 Part 2 (NIR178 Schedule 3)

[figure not shown]
[figure not shown]
Cycle	Day	Scheduled Time Point (h)	Analyte ^b
1	1	Pre-dose (0 h)	NIR178 and NJI765
1	1	15 min post-dose (\pm 5 min)	NIR178 and NJI765
1	1	30 min post-dose (\pm 5 min)	NIR178 and NJI765
1	1	1 h post-dose (\pm 5 min)	NIR178 and NJI765
1	1	1.5 h post-dose (\pm 5 min)	NIR178 and NJI765
1	1	2 h post dose (\pm 10 min)	NIR178 and NJI765
1	1	3 h post-dose (\pm 10 min)	NIR178 and NJI765
1	1	4 h post-dose (\pm 30 min)	NIR178 and NJI765
1	1	8 h post-dose (\pm 30 min)	NIR178 and NJI765
1	2	Pre-dose (0hr/12 hrs post day 1 evening dose)	NIR178 and NJI765
1	7	Pre-dose (0 h)	NIR178 and NJI765
1	7	15 min post-dose (\pm 5 min)	NIR178 and NJI765
1	7	30 min post-dose (\pm 5 min)	NIR178 and NJI765
1	7	1 h post-dose (\pm 5 min)	NIR178 and NJI765
1	7	1.5 h post-dose (\pm 5 min)	NIR178 and NJI765
1	7	2 h post dose (\pm 10 min)	NIR178 and NJI765
1	7	3 h post-dose (\pm 10 min)	NIR178 and NJI765
1	7	4 h post-dose (\pm 30 min)	NIR178 and NJI765
1	7	8 h post-dose (\pm 30 min)	NIR178 and NJI765
1	8	12 hrs post day 7 evening dose	NIR178 and NJI765
EOT ^a		Anytime	NIR178 and NJI765
Unscheduled		Anytime	NIR178 and NJI765

[figure not shown]
[figure not shown]
^a a PK sample collection will occur at cycle 6 or EOT, whichever occurs first
^b Same blood samples collected to assess PK of NIR178 will be used to measure its metabolite NJI765 as both analytes are assayed simultaneously by the analytical laboratory.

[figure not shown]
7.2.3.1 Analytical methods

Concentrations of NIR178 and NJI765 will be determined from incurred plasma samples using a validated LC/MS-MS assay with a lower limit of quantification (LLOQ) of 1.00 ng/mL or lower for both analytes. The quantification of these two analytes for PK characterization will occur simultaneously at a Novartis' designated analytical laboratory and hence does not require collection of a separate blood sample series for each.

Concentrations of PDR001 will be determined from serum using a validated LC/MS-MS assay. Anti-PDR001 antibodies will be determined from serum using validated homogenous ELISA.

[figure not shown]
8 Safety monitoring and reporting

8.1 Adverse events

8.1.1 Definitions and reporting

An adverse event is defined as the appearance of (or worsening of any pre-existing) undesirable sign(s), symptom(s), or medical condition(s) that occur after patient's signed informed consent has been obtained.

Abnormal laboratory values or test results occurring after informed consent constitute adverse events only if they induce clinical signs or symptoms, are considered clinically significant, require therapy (e.g., hematologic abnormality that requires transfusion or hematological stem cell support), or require changes in study medication(s).

Adverse events that begin or worsen after informed consent should be recorded in the Adverse Events CRF. Conditions that were already present at the time of informed consent should be recorded in the Medical History page of the patient's CRF. Adverse event monitoring should be continued for at least 150 days following the last dose of PDR001 or 30 days after the last dose NIR178, whichever occurs later. After initiation of new post-treatment antineoplastic therapy, only AEs suspected to be related to study treatment will be collected in the Adverse Event CRF. Adverse events (including lab abnormalities that constitute AEs) should be described using a diagnosis whenever possible, rather than individual underlying signs and symptoms. When a clear diagnosis cannot be identified, each sign or symptom should be reported as a separate Adverse Event.

Adverse events will be assessed and graded according to the Common Terminology Criteria for Adverse Events (CTCAE) version 4.03.

If CTCAE grading does not exist for an adverse event, the severity of mild, moderate, severe, and life-threatening, death related to the AE corresponding respectively to Grades 1 - 5, will be used. Information about any deaths (related to an Adverse Event or not) will also be collected through a Death form.

The occurrence of adverse events should be sought by non-directive questioning of the patient (subject) during the screening process after signing informed consent and at each visit during the study. Adverse events also may be detected when they are volunteered by the patient (subject) during the screening process or between visits, or through physical examination, laboratory test, or other assessments. As far as possible, each adverse event should be evaluated to determine:

1. The severity grade (CTCAE Grade 1-5)
2. Its duration (Start and end dates)
3. Its relationship to the study treatment (Reasonable possibility that AE is related: No, Yes)
4. Action taken with respect to study or investigational treatment (none, dose adjusted, temporarily interrupted, permanently discontinued, unknown, not applicable)
5. Whether medication or therapy was given (no concomitant medication/non-drug therapy, concomitant medication/non-drug therapy)
6. Whether it is serious, where a serious adverse event (SAE) is defined as in [Section 8.2.1](#) and which seriousness criteria have been met
7. Outcome (not recovered/not resolved, recovered/resolved, recovering/resolving, recovered/resolved with sequelae, fatal, unknown)

If the event worsens the event should be reported a second time in the CRF noting the start date when the event worsens in toxicity. For grade 3 and 4 adverse events only, if improvement to a lower grade is determined a new entry for this event should be reported in the CRF noting the start date when the event improved from having been Grade 3 or Grade 4.

All adverse events should be treated appropriately. If a concomitant medication or non-drug therapy is given, this action should be recorded on the Adverse Event CRF.

Once an adverse event is detected, it should be followed until its resolution or until it is judged to be permanent, and assessment should be made at each visit (or more frequently, if necessary) of any changes in severity, the suspected relationship to the study treatment, the interventions required to treat it, and the outcome.

Progression of malignancy (including fatal outcomes), if documented by use of appropriate method (for example, as per RECIST 1.1 or iRECIST criteria for solid tumors or as per [Cheson et al \(2014\)](#) guidelines for hematological malignancies), should not be reported as a serious adverse event.

Adverse events separate from the progression of malignancy (example, deep vein thrombosis at the time of progression or hemoptysis concurrent with finding of disease progression) will be reported as per usual guidelines used for such events with proper attribution regarding relatedness to the drug.

8.1.2 Laboratory test abnormalities

8.1.2.1 Definitions and reporting

Laboratory abnormalities that constitute an Adverse event in their own right (are considered clinically significant, induce clinical signs or symptoms, require concomitant therapy or require changes in study treatment), should be recorded on the Adverse Events CRF. Whenever possible, a diagnosis, rather than a symptom should be provided (e.g. anemia instead of low hemoglobin). Laboratory abnormalities that meet the criteria for Adverse Events should be followed until they have returned to normal or an adequate explanation of the abnormality is found. When an abnormal laboratory or test result corresponds to a sign/symptom of an already reported adverse event, it is not necessary to separately record the lab/test result as an additional event.

Laboratory abnormalities, that do not meet the definition of an adverse event, should not be reported as adverse events. A Grade 3 or 4 event (severe) as per CTCAE does not automatically indicate a SAE unless it meets the definition of serious as defined below and/or as per investigator's discretion. A dose hold or medication for the lab abnormality may be required by the protocol in which case the lab abnormality would still, by definition, be an adverse event and must be reported as such.

8.2 Serious adverse events

8.2.1 Definitions

Serious adverse event (SAE) is defined as one of the following:

- Is fatal or life-threatening
- Results in persistent or significant disability/incapacity
- Constitutes a congenital anomaly/birth defect
- Is medically significant, i.e., defined as an event that jeopardizes the patient or may require medical or surgical intervention to prevent one of the outcomes listed above
- Requires inpatient hospitalization or prolongation of existing hospitalization,

- Note that hospitalizations for the following reasons should not be reported as serious adverse events:
 - Routine treatment or monitoring of the studied indication, not associated with any deterioration in condition
 - Elective or pre-planned treatment for a pre-existing condition that is unrelated to the indication under study and has not worsened since signing the informed consent
 - Social reasons and respite care in the absence of any deterioration in the patient's general condition
- Note that treatment on an emergency outpatient basis that does not result in hospital admission and involves an event not fulfilling any of the definitions of a SAE given above is not a serious adverse event

8.2.2 Reporting

To ensure patient safety, every SAE, regardless of suspected causality, occurring after the patient has provided informed consent and until at least 150 days after the last dose of PDR001, or 30 days after the last dose of NIR178, whichever occurs later, must be reported to Novartis within 24 hours of learning of its occurrence. If a patient starts a post-treatment antineoplastic therapy, then only SAEs suspected to be related to study treatment will be reported.

Any additional information for the SAE including complications, progression of the initial SAE, and recurrent episodes must be reported as follow-up to the original episode within 24 hours of the investigator receiving the follow-up information. An SAE occurring at a different time interval or otherwise considered completely unrelated to a previously reported one should be reported separately as a new event.

Any SAEs experienced after the 150 day safety evaluation follow-up period should only be reported to Novartis if the investigator suspects a causal relationship to the study treatment.

Information about all SAEs is collected and recorded on the Serious Adverse Event Report Form; all applicable sections of the form must be completed in order to provide a clinically thorough report. The investigator must assess and record the relationship of each SAE to each specific study treatment (if there is more than one study treatment), complete the SAE Report Form in English, and submit the completed form within 24 hours to Novartis. Detailed instructions regarding the SAE submission process and requirements for signatures are to be found in the investigator folder provided to each site.

Follow-up information is submitted in the same way as the original SAE Report. Each re-occurrence, complication, or progression of the original event should be reported as a follow-up to that event regardless of when it occurs. The follow-up information should describe whether the event has resolved or continues, if and how it was treated, whether the blind was broken or not, and whether the patient continued or withdrew from study participation.

If the SAE is not previously documented in the Investigator's Brochure or Package Insert (new occurrence) and is thought to be related to the Novartis study treatment, an oncology Chief Medical Office and Patient Safety (CMO&PS) department associate may urgently require further information from the investigator for Health Authority reporting. Novartis may need to issue an Investigator Notification (IN), to inform all investigators involved in any study with

the same drug that this SAE has been reported. Suspected Unexpected Serious Adverse Reactions (SUSARs) will be collected and reported to the competent authorities and relevant ethics committees in accordance with Directive 2001/20/EC or as per national regulatory requirements in participating countries.

8.3 Emergency unblinding of treatment assignment

Not applicable.

8.4 Pregnancies

To ensure patient safety, each pregnancy occurring while the patient is on study treatment must be reported to Novartis within 24 hours of learning of its occurrence. The pregnancy should be followed up to determine outcome, including spontaneous or voluntary termination, details of the birth, and the presence or absence of any birth defects, congenital abnormalities, or maternal and/or newborn complications.

Pregnancy should be recorded on a Clinical Trial Pregnancy Form and reported by the investigator to the oncology Novartis Chief Medical Office and Patient Safety (CMO&PS). Pregnancy follow-up should be recorded on the same form and should include an assessment of the possible relationship to study treatment any pregnancy outcome. Any SAE experienced during pregnancy must be reported on the SAE Report Form.

[figure not shown]
Pregnancy outcomes should be collected for the female partners of any males who took study treatment in this study and the newborn will be followed up to 12 months after delivery date. Consent to report information regarding these pregnancy outcomes should be obtained from the mother.

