31. Women of child-bearing potential, defined as all women physiologically capable of becoming pregnant, **unless** they are using highly effective methods of contraception during dosing and for 150 days after the last dose of PDR001 or 30 days after the last dose of NIR178, whichever occurs later. Highly effective contraception methods include:
 - Total abstinence (when this is in line with the preferred and usual lifestyle of the subject. Periodic abstinence (e.g., calendar, ovulation, symptothermal, post-ovulation methods) and withdrawal are not acceptable methods of contraception
 - Female sterilization (have had surgical bilateral oophorectomy with or without hysterectomy), total hysterectomy, or tubal ligation at least six weeks before taking study treatment. In case of oophorectomy alone, only when the reproductive status of the woman has been confirmed by follow up hormone level assessment

- Male sterilization (at least 6 months prior to screening). The vasectomized male partner should be the sole partner for that subject
- Use of oral, injected or implanted hormonal methods of contraception or placement of an intrauterine device (IUD) or intrauterine system (IUS), or other forms of hormonal contraception that have comparable efficacy (failure rate <1%), for example hormone vaginal ring or transdermal hormone contraception.

In case of use of oral contraception women should have been stable on the same pill for a minimum of 3 months before taking study treatment.

Women are considered post-menopausal and not of child bearing potential if they have had 12 months of natural (spontaneous) amenorrhea with an appropriate clinical profile (e.g. age appropriate [generally age from 40 to 59 years], history of vasomotor symptoms [e.g. hot flush]) in the absence of other medical justification or have had surgical bilateral oophorectomy (with or without hysterectomy), total hysterectomy, or tubal ligation at least six weeks ago. In the case of oophorectomy alone, only when the reproductive status of the woman has been confirmed by follow up hormone level assessment is she considered not of child bearing potential.

32. Sexually active males unless they use a condom during intercourse while taking drug and 30 days after stopping NIR178. Sexually active males should not father a child in this period.

6 Treatment

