7.1.5 Follow up for safety evaluations

All patients receiving PDR001 must have safety evaluations for 150 days after the last dose of PDR001 or 30 days after the last dose of NIR178, whichever occurs later. The follow-up evaluations can be done either by telephone call or visit for the 30-, 90-, and 150-day safety follow-up visits.

Concomitant medications will be collected until the 30-day safety follow-up has been completed or the start of a new antineoplastic therapy, whichever occurs first. Adverse events should be captured on the appropriate eCRF for 150 days after the last dose of medication. If resolution of an adverse event continues past this timeframe, the investigator will still be responsible to undertake appropriate actions, but that information will not be entered into the clinical database. After initiation of a new post-treatment antineoplastic therapy, only AEs and SAEs suspected to be related to study treatment will be recorded in the Adverse Event CRF.

Data collected should be added to the Adverse Events CRF, the antineoplastic therapies since discontinuation of study treatment CRF, and the Concomitant Medications CRF. For female patients of child bearing potential, pregnancy tests will be performed as outlined in [Section 7.2.2.5.7](#).

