Pregnancy Test	If the patient is a woman of child-bearing potential, a serum pregnancy test should be performed at screening, monthly during the study, and at the end of treatment. A serum or urine pregnancy test should be performed monthly during the safety follow-up period.

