7.2.2.5.7 Pregnancy and assessments of fertility

A serum pregnancy test must be performed at screening, every month during the study and at the end of treatment visit. If the screening pregnancy test is performed within 72 hours of cycle 1 day 1, pregnancy test does not have to be repeated.

Every month during the safety follow-up period and at the end of the safety follow-up period, a serum or urine pregnancy test must be performed. If the patient is not coming to the clinic during the safety follow-up, it can be performed at home or at a local doctor's office, and the results will be communicated to the site staff. These follow-up pregnancy tests will be recorded only in the source documentation, not in the CRF.

A pregnancy test is only needed if the patient is a woman of child-bearing potential.

During the COVID-19 pandemic, if the patient cannot visit the site to have serum pregnancy tests done, locally available urine pregnancy test kits may be used. Relevant patients can perform the urine pregnancy test at home and report the result to the site. It is important that patients are instructed to perform the urine pregnancy test first and only if the test result is negative proceed with the administration of the study treatment. A communication process should be established with the patient so that the Site is informed of the pregnancy test results.

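### Section 8.4 sets no explicit duty to report a female patient's pregnancy conceived after treatment ends, although contraception, pregnancy testing and SAE reporting continue to 150 days after PDR001 or 30 days after NIR178, whichever is later

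*Protocol*

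**What the plan says.** Section 8.4 (Pregnancies) sets the reporting duty: "each pregnancy occurring while the patient is on study treatment must be reported to Novartis within 24 hours of learning of its occurrence". The pregnancy is then followed to its outcome, and a second paragraph sends it to the sponsor's safety department on a pregnancy form. The section does not define being on study treatment and gives no period after the last dose.

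Other sections keep the window open for longer. Section 5.3, criterion 31, requires highly effective contraception "during dosing and for 150 days after the last dose of PDR001 or 30 days after the last dose of NIR178, whichever occurs later". Section 7.1.5 sets the safety follow-up: "All patients receiving PDR001 must have safety evaluations for 150 days after the last dose of PDR001", or 30 days after NIR178 if that is later. Section 7.2.2.5.7 adds testing: "Every month during the safety follow-up period and at the end of the safety follow-up period, a serum or urine pregnancy test must be performed". Table 7-6 also asks for monthly tests in that period. Section 8.2.2 requires SAE reporting to at least the same end point.

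The protocol is inconsistent on where follow-up test results are recorded. Section 7.2.2.5.7 says: "These follow-up pregnancy tests will be recorded only in the source documentation, not in the CRF". Tables 7-1, 7-2 and 7-3 give the pregnancy test category D and an X in the follow-up column. Section 7.1 defines D as data entered in the clinical database.

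The SAP has no rule on pregnancy reporting.

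**The concern.** The protocol treats the months after the last dose as a time of possible fetal risk and tests women for pregnancy throughout. Reporting of a patient's own pregnancy is the one linked duty that is tied to treatment and not to that window. A site could find a positive test in follow-up, in a woman who conceived after stopping, and meet no sentence that tells it to notify the sponsor within 24 hours or to follow the pregnancy to outcome.

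What is at stake is fetal and maternal safety information on an investigational combination. Section 11.3 says that women are to be told the medication may carry unknown fetal risks. No efficacy analysis is affected.

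**Working it through.** No sample size or test statistic is involved. The check sets the windows side by side and then measures the gap.

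| Duty | Where | Runs until |
|---|---|---|
| Contraception | 5.3, criterion 31 | later of PDR001 + 150 days and NIR178 + 30 days |
| Safety evaluations | 7.1.5 | the same |
| Pregnancy tests | 7.2.2.5.7, Table 7-6 | monthly through safety follow-up; 7.2.2.5.7 adds one at its end |
| SAE reporting | 8.2.2 | at least the same; suspected-related only once new antineoplastic therapy starts |
| Report of patient's pregnancy | 8.4 | while on study treatment (undefined) |

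**Size of the gap.** Let g be the number of days by which the last NIR178 dose follows the last PDR001 dose. Counting from the last PDR001 dose, the risk window ends at day max(150, g + 30), and the last dose of study treatment falls on day g.

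- Literal reading, covered to the last dose: uncovered time = max(150, g + 30) − g = max(150 − g, 30).
- Analysis reading, covered to 30 days after the last dose of either drug (protocol 10.5.2.1; SAP 2.1.1.2 and 2.1.1.5): uncovered time = max(150 − g, 30) − 30 = max(120 − g, 0).

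| g | Literal | Analysis reading |
|---|---|---|
| 0 (PDR001 given last) | 150 days | 120 days (days 31–150) |
| 27 (NIR178 taken to day 28 of the last cycle) | 123 days | 93 days |
| 120 or more (long NIR178 monotherapy) | 30 days | 0 days |

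The last row is possible because section 6.2.1 allows a patient to continue on either drug alone. For patients who stop both drugs at about the same time, a gap of several months remains on either reading. With a month taken as 30 days, 150/30 = 5 monthly tests fall in the full window, and 120/30 = 4 in days 31 to 150.

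**Which pregnancies fall in the gap.** The duty attaches to when the pregnancy occurs, and the 24-hour clock starts when it becomes known. A pregnancy conceived on treatment and first found in follow-up is therefore inside section 8.4. One conceived after treatment ends is not.

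**Whether another route closes it.** Section 8.2.1 lists congenital anomaly as an SAE criterion, but not pregnancy itself. A pregnancy conceived after the last dose would normally reach term after day 150. By then section 8.2.2 narrows the duty: "Any SAEs experienced after the 150 day safety evaluation follow-up period should only be reported to Novartis if the investigator suspects a causal relationship". Section 14.2.31 lists pregnancy as a reason for ending post-treatment follow-up, but a disposition entry is neither a 24-hour report nor outcome follow-up. The same holds for a database entry under Tables 7-1 to 7-3.

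**The case against.** The strongest reply is that section 8.4 does not forbid later reporting. Its second paragraph, on the pregnancy form, carries no time limit of its own, so a careful site would report anyway. That is a possible reading. But the paragraph follows the sentence that defines which pregnancies are meant and reads as the procedure for those. It also sets no 24-hour clock.

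Other parts of the reply stand and limit the point:

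- A reader might infer that every pregnancy found in follow-up escapes the duty. The documents do not support this, because conception on treatment with later detection is already covered.
- A reader might take the whole 150 days as uncovered in every patient. Section 8.4 leaves its key phrase undefined, NIR178 may continue after PDR001 stops, and the analysis on-treatment period adds 30 days.
- Partner pregnancies are collected with no on-treatment limit, so the gap concerns female patients only.
- A reader might conclude that all information on these cases is lost. In fact section 8.4 requires any SAE during a pregnancy to be reported, and a congenital anomaly suspected to be related remains reportable after day 150.
- Section 7.2.2.5.7 taken alone suggests that follow-up results never reach the database. Tables 7-1 to 7-3 say otherwise, so the defect there is a contradiction.

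**Conclusion.** The point holds in a limited form. A female patient's pregnancy conceived after treatment ends, but inside the protocol's own risk window, has no explicit duty of 24-hour reporting or outcome follow-up. The uncovered time is at most 150 days. Days 31 to 150 remain if the analysis on-treatment period is used and PDR001 is the last drug given. It shrinks if NIR178 is continued alone, and on the analysis reading it closes once NIR178 runs 120 days or more past PDR001.

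This rests on two assumptions: that occurrence in section 8.4 means conception or presence of the pregnancy and not its detection, and that the form paragraph applies to the pregnancies defined just before it. The documents give no expected number of cases. It is probably small, and no primary analysis depends on it. The change is still worth making, because the stated rule itself leaves out post-treatment conceptions that the protocol tests for.

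**What to change.** 1. In section 8.4, extend the period for reporting a patient's pregnancy so that it ends where the contraception and SAE rules end: 150 days from the final PDR001 dose or 30 days from the final NIR178 dose, taking the later date.
2. In section 7.2.2.5.7, state that a positive follow-up test is reported under section 8.4 on the pregnancy form.
3. Reconcile the source-only recording in section 7.2.2.5.7 with category D and the follow-up X in Tables 7-1 to 7-3.

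The cost is a few lines of text and at most a few more pregnancy forms, with no new test or visit. SAP section 4 says the study is being closed out. Women who stop treatment still enter this window, apart from those who transfer to another study or alternative treatment under section 7.1.5.1, so the change matters for as long as any are in safety follow-up.
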